8.4.17 Patient Global Impression of HS Severity (PGI-S-HS)

The PGI-S-HS is a single item to assess study participants perceptions of the overall severity of HS over the past 7 days (none, mild, moderate, severe, very severe).

The number and percentage of participants with each response will be summarized for each visit by treatment group based on OC data.

The number and percentage of participants that complete the PGI-S-HS will be calculated for each visit by treatment group. The percentage will be based on the number of participants in the RS. The summary will be repeated where the percentage is based on the subset of participants who complete each particular visit. A participant will be considered a completer at a visit if the response is nonmissing at that visit.

8.4.18 Patient Global Impression of Change in HS Severity (PGI-C-HS)

The PGI-C-HS is a single item to assess study participants perception of the change in HS since they started taking the study medication (much better, a little better, no change, a little worse, much worse).

The number and percentage of participants with each response will be summarized for each visit by treatment group based on OC data.

The number and percentage of participants that complete the PGI-C-HS will be calculated for each visit by treatment group. The percentage will be based on the number of participants in the RS (or MS, as appropriate). The summary will be repeated where the percentage is based on the subset of participants who complete each particular visit. A participant will be considered a completer at a visit if the response is nonmissing at that visit.

8.4.19 Patient Global Impression of Severity of Skin Pain (PGI-S-SP)

The PGI-S-SP is a single item to assess study participants' perceptions of the severity of their skin pain from their HS lesions, over the past 7 days (none, mild, moderate, severe, very severe).

The number and percentage of participants with each response will be summarized for each visit by treatment group based on OC data.

The number and percentage of participants that complete the PGI-S-SP will be calculated for each visit by treatment group. The percentage will be based on the number of participants in the RS (or MS, as appropriate). The summary will be repeated where the percentage is based on the subset of participants who complete each particular visit. A participant will be considered a completer at a visit if the response is nonmissing at that visit.

8.4.20 Patient Global Impression of Change in Severity of Skin Pain (PGI-C-SP)

The PGI-C-SP is a single item to assess study participants' perceptions of change in their skin pain from their HS lesions, since they started taking the study medication (much better, a little better, no change, a little worse, much worse).

The number and percentage of participants with each response will be summarized for each visit by treatment group based on OC data.

The number and percentage of participants that complete the PGI-C-SP will be calculated for each visit by treatment group. The percentage will be based on the number of participants in the RS. The summary will be repeated where the percentage is based on the subset of participants who complete each particular visit. A participant will be considered a completer at a visit if the response is nonmissing at that visit.

8.4.21 Euro-Quality of Life 5-Dimensions, 3 levels (EQ-5D-3L)

The EQ-5D-3L comprises 5 questions on mobility, self-care, pain, usual activities, and psychological status with 3 possible answers for each item (1=no problem, 2=moderate problem, 3=severe problem). In addition, there is a VAS to indicate the general health status with 100 indicating the best health status.

Change from Baseline in EQ-5D-3L VAS scores is defined as Post-Baseline EQ-5D-3L VAS score minus Baseline EQ-5D-3L VAS score.

Responses to EQ-5D-3L will be summarized based on OC only as primary analysis. No imputation is applied to responses to EQ-5D-3L but is applied to EQ-5D-3L VAS scores.

Changes from Baseline in EQ-5D-3L VAS will be summarized using descriptive statistics by treatment group and visit. The table will display descriptive statistics for the Baseline, followed by descriptive statistics for the change from Baseline for all visits.

The number and percentage of participants with each response in the EQ-5D-3L will be summarized for each visit by treatment group based on OC data.

The number and percentage of participants that complete the EQ-5D-3L will be calculated for each visit by treatment group. The percentage will be based on the number of participants in the RS. The summary will be repeated where the percentage is based on the subset of participants who complete each particular visit. A participant will be considered a completer at a visit if each of the domains and VAS are completed at that visit.

8.4.22 Work Productivity and Activity Impairment Questionnaire-Specific Health Problem (WPAI-SHP) v2.0 adapted to HS scores

The WPAI-SHP V2.0 is a patient-reported questionnaire that assesses study participant's employment status, work absenteeism, work impairment while working (presenteeism), overall work, and daily activity impairment attributable to a specific health problem. It has been used in several clinical studies of biologic therapy in participants with plaque PSO.

Five out of 6 items of the WPAI-SHP are regrouped into the 4 dimensions, with scores expressed as percentage, where higher numbers indicate greater impairment and less productivity, ie, worse outcomes, as described in the WPAI-SHP scoring rules.

The scoring rules for the WPAI-SHP are as follows:

Questions:

- 1 = currently employed
- 2 = hours missed due to specified problem
- 3 = hours missed other reasons
- 4 = hours actually worked

- 5 = degree problem affected productivity while working
- 6 = degree problem affected regular activities

Scores:

- Percent work time missed due to problem: $[Q2 \text{ hours}/(Q2 \text{ hours} + Q4 \text{ hours})]*100$
- Percent impairment while working due to problem: $[Q5 \text{ score}/10]*100$
- Percent overall work impairment due to problem: $[Q2 \text{ hours}/(Q2 \text{ hours} + Q4 \text{ hours}) + [(1 - (Q2 \text{ hours}/(Q2 \text{ hours} + Q4 \text{ hours}))) \times (Q5 \text{ score}/10)]]*100$
- Percent activity impairment due to problem: $[Q6 \text{ score}/10]*100$

A negative number will indicate a reduction in the score/improvement for participants.

The change from Baseline score is derived as post Baseline score minus Baseline score. A negative change score indicates a reduction in the score/improvement for the participant.

Summary statistics of the actual values and change from Baseline values will be used to summarize WPAI-SHP for each visit by treatment group. The table will display descriptive statistics for the Baseline, followed by descriptive statistics for the change from Baseline for all visits.

Missing data for the continuous change from Baseline will be handled by using MI via the MCMC and monotone regression method specified in Section 4.2.1.3.

The number and percentage of participants that complete the WPAI-SHP will be calculated for each visit by treatment group. The percentage will be based on the number of participants in the RS. The summary will be repeated where the percentage is based on the subset of participants who complete each particular visit. A participant will be considered a completer at a visit if the percentages in each dimension are calculated at that visit.

A by-participant listing of the WPAI-SHP questionnaire, WPAI-SHP domains and change from Baseline will be provided.

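### The WPAI rules in Section 8.4.22 never use employment status: participants without a job cannot count as completers, and work scores are imputed for those who stop working after Baseline

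*SAP*

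**What the plan says.** Section 8.4.22 lists six WPAI items, the first being "1 = currently employed". It then gives four scores:

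- work time missed, from items 2 and 4 (hours missed because of HS and hours actually worked);
- impairment while working, from item 5;
- "Percent overall work impairment due to problem", from items 2, 4 and 5;
- activity impairment, from item 6 alone.

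Item 1 enters no formula and no rule.

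On completion, the section states: "A participant will be considered a completer at a visit if the percentages in each dimension are calculated at that visit". On the denominator: "The percentage will be based on the number of participants in the RS". The table is then repeated with visit attenders as the denominator.

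On missing data: "Missing data for the continuous change from Baseline will be handled by using MI via the MCMC and monotone regression method", with a pointer to Section 4.2.1.3. That section imputes other continuous endpoints by multiple imputation, with LOCF if the model does not converge. Table 4-2 names the work scores among the imputed variables, with a range of 0 to 100.

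**The concern.** A work score does not exist for someone who is not working. Its absence is a fact about the participant, not a failure of data collection. The plan treats it as a failure twice: once when it counts completed questionnaires, and once when it fills in absent values under a missing-at-random assumption.

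Two descriptive outputs are at stake. The completion table is meant to show data quality, but it would partly measure unemployment. The change-from-Baseline tables for the work dimensions would include model-based values, as if still at work, for people who had left work. Leaving work because of HS is itself an outcome that a productivity measure ought to show.

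Elsewhere the SAP deals with the same kind of problem. HiSQOL (Table 8-5) has a scored response for people who do not work or study. DLQI (Table 8-3) scores items that are not relevant. The DLQI MCID analysis (Section 8.4.15) is limited to participants who can reach the threshold. WPAI has no equivalent rule.

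**Working it through.** The plan states no figure on this point, so there is none to reproduce. The check compares its rules and adds simple arithmetic.

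**Which scores can be calculated (formulas from Section 8.4.22).** With no work hours, items 2 and 4 are both 0:

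- Work time missed: 0/(0 + 0), undefined.
- Overall work impairment: contains the same ratio, so undefined.
- Impairment while working: item 5 concerns productivity at work, so it has no input for someone without a job.
- Activity impairment: item 6 / 10 × 100. An answer of 5 gives 50%.

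A participant without a job has one score out of four. An employed participant with zero hours in both items lacks at least two.

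**Completion.** The rule needs all four percentages, so neither participant can be a completer, however fully the form is answered. The highest possible completion rate in the Randomized Set is:

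ceiling = participants with calculable work scores / participants randomized

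The planned number randomized is 490 (Section 2.3.4). The employed share is not in the SAP, so the values below are assumptions. They also suppose that every form is fully answered and that every employed participant has some work hours.

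| Assumed share employed | Employed of 490 | Ceiling |
|---|---|---|
| 50% | 245 | 50% |
| 60% | 294 | 60% |
| 70% | 343 | 70% |
| 80% | 392 | 80% |

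The same holds for the second denominator, with the employed share among visit attenders in place of the share in the Randomized Set.

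**Imputation.** Four provisions have to be read together:

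1. Sections 8.4.22 and 4.2.1.3 and Table 4-2 send absent work scores to multiple imputation, with no exception for values that do not apply.
2. The imputation model in Section 4.2.2.1 holds Hurley Stage, Baseline antibiotic use and the variable's own values over time. Employment status cannot inform it.
3. Section 3.9 does not list loss of employment as an intercurrent event, so no estimand calls for replacing these values.
4. Section 4.2.2.1, continuous endpoints, step 2, derives change from the observed Baseline value and the observed or imputed later value.

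Taken together:

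- **No work score at Baseline:** no change score is derived.
- **Work score at Baseline, not working later:** the later work scores are blank, are imputed, and enter the change summary. If the model fails, LOCF carries forward the last available score.

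The size of the second group depends on how many participants leave work during the study. The SAP gives nothing from which to estimate it.

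**The case against.** The strongest reply is that the reach of the imputation problem is easily exaggerated. A reader might multiply 490 by the non-employed share and infer that 98 to 245 participants carry invented work scores at each visit. The documents do not support that. The figure counts everyone without a job, whereas change is derived only from an observed Baseline value. A reader might also infer that the results describe a population in which everyone works, or that scores are reported for people who never worked. Section 8.4.22 mentions summaries of actual values, but it lays the table out as Baseline statistics followed by change. On that layout, participants with no Baseline work score contribute nothing to the work dimensions. This part of the reply stands.

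Other replies stand in part:

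- **Scoring rules.** The section refers to the WPAI-SHP scoring rules, which might carry an employment condition. But the SAP then writes the rules out without one, and the completion and imputation rules are its own.
- **Listing.** A by-participant listing of the questionnaire will contain item 1, so job loss is not concealed. It is simply not tabulated.
- **Conditioning.** Limiting change to people employed at the visit conditions on a post-randomization outcome and drops those who lost work. This is a fair warning about the remedy, and it is why an employment table has to accompany it.

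None of these replies answers the completion rule.

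**Conclusion.** The point holds in two parts.

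**Completion.** This follows directly from the text. Participants without a job, or with zero hours in items 2 and 4, cannot be completers, and the reported rate is capped at the share with calculable work scores. The cap of 50% to 80% rests on an assumed employment range and is an illustration.

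**Imputation.** The plan has no rule separating not applicable from missing. The clearly affected group is participants with an observed Baseline work score who later have no job or no work hours. Its size cannot be estimated from the SAP.

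The severity is minor. WPAI is among the other efficacy endpoints (Section 2.2.1.3), is summarized descriptively, and appears neither in the testing sequence of Section 4.5 nor in the nominal p-value list of Section 8.5. The primary conclusion, the type I error control and the power are unaffected.

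**What to change.** In Section 8.4.22, with a matching note to Table 4-2:

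1. Define a completer as a participant who has answered all items that apply given item 1. Alternatively, report completion of the work dimensions among those employed at the visit, and completion of activity impairment among all participants.
2. Treat the work scores as not applicable at visits where item 1 is no or where items 2 and 4 sum to zero hours, and do not impute them there, whether by multiple imputation or LOCF.
3. Tabulate employment status (item 1) by visit and arm, so that job loss is shown beside the change scores.

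The cost is a few lines of SAP text and some programming. No new data are needed, because item 1 is already collected. The price is a smaller n for the work dimensions and a change summary that is conditional on working at the visit, so the third step should not be left out.

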8.4.23 Treatment Satisfaction Questionnaire – Medication-9

The TSQM-9 is an abbreviated 9-item version of the TSQM, excluding the side effects of medication domain. The domains included in the TSQM-9 include effectiveness (3 items), convenience (3 items) and global satisfaction (3 items). The TSQM-9 domain scores range from 0 to 100 with higher scores representing higher satisfaction.

The scores for each measure are as follows:

- Global Satisfaction:
 - If no items are missing: $([\text{Sum}(Item 7 to Item 9) - 3]/14)*100$
 - If either Item 7 or 8 is missing: $([\text{Sum}(the two completed items)) - 2]/10)*100$
 - If Item 9 is missing: $([\text{Sum}(Item 7 and Item 8))-2]/8)*100$
- Effectiveness
 - If no items are missing: $([Item 1 + Item 2 + Item 3) - 3]/18)*100$

- If one item is missing: $([(\text{Sum}(\text{the two completed items}) - 2]/12)*100$
- Convenience
 - If no items are missing: $([\text{Sum}(\text{Item 4 to Item 6}) - 3]/18)*100$
 - If one item is missing: $([\text{Sum}(\text{the two completed items}) - 2]/12)*100$

Frequency tables will be produced to summarize answers provided to each of the 9 items of the TSQM-9 at Weeks 16 and 48 by treatment group. Responses to TSQM-9 will be summarized based on OC. No imputation will be applied.

The number and percentage of participants that complete the TSQM-9 will be calculated for each visit by treatment group. The percentage will be based on the number of participants in the RS. The summary will be repeated where the percentage is based on the subset of participants who complete each particular visit. A participant will be considered a completer at a visit if each of the domains are completed at that visit.

A by-participant listing of TSQM-9 will be provided.

8.4.24 Lesion intervention

Investigators will have the option to perform interventions in the event an acutely painful lesion occurs that requires immediate intervention.

The following rules will be used to assign a lesion intervention to a study period:

- **Initial Treatment Period:** a lesion intervention will be assigned to the Initial Treatment Period if it has been performed between the first administration of IMP on Day 1 up to and including Week 16.
- **Maintenance Treatment Period:** a lesion intervention will be assigned to the Maintenance Treatment Period if it has been performed between Week 16 through the Week 48 visit.

Methods for dealing with partial dates are specified in Section 4.2.4.

A listing of participants who receive any lesion intervention will be provided.

The number and percentage of participants who receive at least 1 lesion intervention will be summarized by treatment group for the Initial Treatment Period, Maintenance Treatment Period, and the combined Initial and Maintenance Treatment Period.

The number and percentage of participants with 2, 3, and 4 or more lesion interventions will also be summarized by treatment group for the Initial Treatment Period, Maintenance Treatment Period, and the combined Initial and Maintenance Treatment Period.

The number and percentage of participants with 2 or more lesion interventions performed on the same lesion will be summarized by treatment group for the Initial Treatment Period, Maintenance Treatment Period, and the combined Initial and Maintenance Treatment Period.

8.5 Additional statistical analyses of other efficacy endpoints

For selected other efficacy variables, it is of interest to perform statistical tests and to calculate inferential statistics. As these tests are not part of the multiplicity-controlled procedure, the associated p-values are considered nominal and are not controlled for multiplicity.

For binary variables, the analysis will follow what was specified for the primary analysis of the primary endpoint and the corresponding p-value reported. Missing values will be imputed as for the primary analysis. For continuous variables, the MI – MCMC / Monotone Regression approach used for the secondary continuous endpoint will be applied for the imputation model. The analysis model will be as for the corresponding secondary continuous endpoint analysis, unless otherwise indicated.

Below is a list of variables for which these nominal p-values will be calculated. The results of these inferential tests will be presented in a single table summarizing the testing performed outside of the multiplicity-controlled testing procedure.

All tests will be for both 320mg Q2W vs Placebo and 320mg Q4W vs Placebo (tested separately) and will be performed for the Week 12 and Week 16 visits only. If the Week 16 visit test is already part of the controlled testing procedure in the primary or secondary analyses, only Week 12 is indicated here.

- HiSCR₅₀ at Week 12
- HiSCR₇₅ at Week 12
- HiSCR₉₀
- HiSCR₁₀₀
- Flare by Week 12
- Flare by Week 16
- Time to flare by Week 12 (based on time-to-event analysis per Section 8.4.5 and adjusted appropriately)
- IHS4 change from Baseline
- IHS4 percentage change from Baseline
- HS Physician's Global Assessment: rate of participants who are Clear or Mild
- DLQI total score change from Baseline at Week 12
- Worst Skin Pain per HSSDD change from Baseline at Week 12
- Skin Pain response per HSSDD at Week 12

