8.4.8 HS-Physician's Global Assessment 6-point scale

The HS-Physician's Global Assessment is a validated 6-point scale that is used to measure improvement in inflammatory nodules, abscesses, and draining tunnels. The HS-Physician's Global Assessment scale is defined in [Table 8-4](#).

Table 8-4: HS-Physician's Global Assessment 6-point scale

Score	Rating	Description
0	Clear	No abscesses, no draining tunnels (fistulas/sinus tracts), no nodules
1	Minimal	No abscesses, no draining tunnels (fistulas/sinus tracts), no inflammatory nodules, presence of non-inflammatory nodules
2	Mild	No abscesses or draining tunnels (fistulas/sinus tracts), and less than 5 inflammatory nodules, or Single abscess or draining tunnel (fistula/sinus tract), and no inflammatory nodules
3	Moderate	No abscesses or draining tunnels (fistulas/sinus tracts), and at least 5 inflammatory nodules, or Single abscess or draining tunnel (fistula/sinus tract) in the presence of inflammatory nodules, or Between 2 and 5 abscesses or draining tunnels (fistulas/sinus tracts) with or without inflammatory nodules, up to 10
4	Severe	Between 2 and 5 abscesses and draining tunnels (fistulas/sinus tracts), with inflammatory nodules that are greater than 10
5	Very severe	More than 5 abscesses or draining tunnels (fistulas/sinus tracts)

The gradings will be derived on a participant-level basis (ie, across all anatomical regions) based on the following rules:

- Clear:
 - number of abscesses = 0;
 - number of draining tunnels (fistulas/sinus tracts) = 0;
 - number of inflammatory nodules = 0;
 - number of non-inflammatory nodules = 0;
 - number of non-draining tunnels (fistulas/sinus tracts) – no limit;
 - number of HS scars – no limit;
- Minimal:
 - number of abscesses = 0;
 - number of draining tunnels (fistulas/sinus tracts) = 0;
 - number of inflammatory nodules = 0;
 - number of non-inflammatory nodules ≥ 1 ;
 - number of non-draining tunnels (fistulas/sinus tracts) – no limit;
 - number of HS scars – no limit;
- Mild:

- number of abscesses = 0;
- number of draining tunnels (fistulas/sinus tracts) = 0;
- number of inflammatory nodules ≥ 1 and ≤ 4 ;
- number of non-inflammatory nodules – no limit;
- number of non-draining tunnels (fistulas/sinus tracts) – no limit;
- number of HS scars – no limit;

OR

- sum of number of abscesses and number of draining tunnels (fistulas/sinus tracts) = 1;
- number of inflammatory nodules = 0;
- number of non-inflammatory nodules – no limit;

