- number of non-draining tunnels (fistulas/sinus tracts) – no limit;
- number of HS scars – no limit;

- **Moderate:**

- number of abscesses = 0;
- number of draining tunnels (fistulas/sinus tracts) = 0;
- number of inflammatory nodules ≥ 5 ;
- number of non-inflammatory nodules – no limit;
- number of non-draining tunnels (fistulas/sinus tracts) – no limit;
- number of HS scars – no limit;

OR

- sum number of abscesses and number of draining tunnels (fistulas/sinus tracts) = 1;
- number of inflammatory nodules ≥ 1 ;
- number of non-inflammatory nodules – no limit;
- number of non-draining tunnels (fistulas/sinus tracts) – no limit;
- number of HS scars – no limit;

OR

- sum of number of abscesses and number of draining tunnels (fistulas/sinus tracts) ≥ 2 and ≤ 5 ;
- number of inflammatory nodules ≤ 10 ;
- number of non-inflammatory nodules – no limit;
- number of non-draining tunnels (fistulas/sinus tracts) – no limit;
- number of HS scars – no limit;

- Severe:
 - sum of number of abscesses and number of draining tunnels (fistulas/sinus tracts) ≥ 2 and ≤ 5 ;
 - number of inflammatory nodules > 10 ;
 - number of non-inflammatory nodules – no limit;
 - number of non-draining tunnels (fistulas/sinus tracts) – no limit;
 - number of HS scars – no limit;
- Very Severe:
 - sum of number of and number of draining tunnels (fistulas/sinus tracts) > 5 ;
 - number of inflammatory nodule – no limit;
 - number of non-inflammatory nodules – no limit;
 - number of non-draining tunnels (fistulas/sinus tracts) – no limit;
 - number of HS scars – no limit

The number and percentage of participants at each level of the assessment scale (Clear, Minimal, Mild, Moderate, Severe and Very severe) will be presented by treatment group and visit. The denominator for the percentages will be based on the number of participants in the given treatment group and visit for which there are no missing data for the HS-Physician's Global Assessment.

Shift tables for the changes from Baseline in this scale will be presented for each post-Baseline visit by treatment group. The denominator for the percentages will be based on the number of participants in the given treatment group and visit for which there is no missing data for the change from Baseline in HS-Physician's Global Assessment.

The HS-Physician's Global Assessment will be listed by treatment group and participant at each visit.

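### As worded, the tested HS-Physician's Global Assessment response takes scores 0 and 2 and leaves out Minimal (score 1), which ranks better than Mild

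*SAP*

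**What the plan says.** Section 8.5 of the SAP names selected other efficacy variables for inferential testing. One entry is the HS-Physician's "Global Assessment: rate of participants who are Clear or Mild". The section adds three things that matter here:

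- Analysis: "For binary variables, the analysis will follow what was specified for the primary analysis of the primary endpoint".
- Timing: the tests "will be performed for the Week 12 and Week 16 visits only", separately for 320mg Q2W and 320mg Q4W against placebo.
- Status: "the associated p-values are considered nominal and are not controlled for multiplicity".

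Section 8.4.8 and Table 8-4 define the scale. Its levels, in order, are "Clear, Minimal, Mild, Moderate, Severe and Very severe", scored 0 to 5. Clear is described as "No abscesses, no draining tunnels (fistulas/sinus tracts), no nodules". Minimal is "No abscesses, no draining tunnels (fistulas/sinus tracts), no inflammatory nodules, presence of non-inflammatory nodules". The first branch of Mild is "No abscesses or draining tunnels (fistulas/sinus tracts), and less than 5 inflammatory nodules"; the second is a single abscess or draining tunnel without inflammatory nodules.

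For this scale, Section 8.4.8 plans frequency tables of all six levels and shift tables from Baseline. Section 2.2.1.3 lists only the change from Baseline. Neither defines a responder.

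**The concern.** A responder variable built on an ordered severity scale should be a cut: everyone at or below some score responds, everyone above it does not. The entry in Section 8.5 joins two levels that are not adjacent. If it is programmed as written, the better of two outcomes can be the one that counts against a participant, and the odds ratio no longer measures improvement on the scale.

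Because Section 8.5 holds the only responder definition for this scale, a programmer has nothing else in the SAP to follow. If the problem is noticed only once treatment codes are known, someone must then choose between two plausible corrections with the results in view.

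**Working it through.** No sample size, power or alpha figure depends on this point, so there is no stated figure to reproduce. The check is to map the wording in Section 8.5 onto the derivation rules in Section 8.4.8 (R = responder, N = nonresponder).

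| Score | Category | Lesion counts under the rules | As worded | If 0-1 meant | If 0-2 meant |
|---|---|---|---|---|---|
| 0 | Clear | no abscess, draining tunnel or nodule of either kind | R | R | R |
| 1 | Minimal | as Clear, but at least 1 non-inflammatory nodule | N | R | R |
| 2 | Mild | 1 to 4 inflammatory nodules without abscess or draining tunnel; or 1 abscess or draining tunnel without inflammatory nodules | R | N | R |
| 3-5 | Moderate to Very severe | higher counts | N | N | N |

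**Step 1, ordering.** Minimal has no abscess, draining tunnel or inflammatory nodule. Mild always has at least one of these. Minimal is therefore the better state, and the as-worded column runs R, N, R, N. It is not monotone in severity.

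**Step 2, comparison with another row of the same list.** HiSCR₁₀₀ is also tested in Section 8.5. Take a participant with a Baseline AN count above zero who reaches an AN count of 0 with no draining tunnels and has one non-inflammatory nodule left. This participant is a HiSCR₁₀₀ responder but, as worded, a nonresponder on the global assessment. A participant with four inflammatory nodules and no abscess or draining tunnel has an AN count of 4, so is not a HiSCR₁₀₀ responder, yet is a responder on the global assessment.

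**Step 3, effect on the comparison.** For one arm at one visit, after intercurrent events are set to nonresponse and missing values imputed, let C, M and D be the proportions Clear, Minimal and Mild. Subscripts B and P denote bimekizumab and placebo.

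- As worded, the response rate is C + D.
- If 0-2 was meant, the target is C + M + D. The error in the rate is −M, and the error in the treatment difference is −(M_B − M_P).
- If 0-1 was meant, the target is C + M. The error in the rate is D − M, and the error in the difference is (D_B − D_P) − (M_B − M_P).

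The SAP gives no values for M or D in any arm, so neither sign nor size can be computed. Equal Minimal rates would leave the difference unchanged in the 0-2 case, though in general not the odds ratio.

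**Step 4, reach.** Two doses × two visits = 4 reported comparisons.

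**The case against.** The best defence is that this is one bullet in a list of variables, not a derivation. The SAP never says that Minimal counts as failure, and the wording looks like a slip that a programmer would query. The consequences are also small. The endpoint sits among the other efficacy endpoints, outside the sequence in Section 4.5, and Section 3.10 says that the nominal p-values should not be used to declare statistical significance. Section 8.4.8 already tabulates all six categories by treatment group and visit, so a reader could add up either range.

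Most of this stands. A reader might infer that the sponsor chose a non-monotone response on purpose; nothing in the SAP supports that. The defence does not remove the need for a correction. There are two natural repairs, and they are materially different endpoints, because 0-2 admits participants with up to four inflammatory nodules or a single abscess and 0-1 does not. The frequency tables use participants with non-missing data only, so they do not supply the imputed comparison, odds ratio or p-value.

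A reader might also infer that the wording understates the drug's effect. For example, if 5-10% of bimekizumab participants and 2% of placebo participants were Minimal, the difference would be understated by 5 − 2 = 3 to 10 − 2 = 8 percentage points. The SAP does not support this as a finding. Those rates are assumptions found nowhere in it, and the formula holds only if 0-2 was intended. With more Minimal participants on placebo than on bimekizumab, the same formula gives an overstatement. If 0-1 was intended, the Mild rates enter as well.

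**Conclusion.** The point holds as an error of wording that needs correcting. Taken literally, the response in Section 8.5 omits Minimal while including the worse category Mild, and nothing else in the SAP repairs it. The intended definition is probably 0-1 or 0-2; the SAP does not show which.

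The reach is four nominal comparisons, which could be distorted in either direction. The size depends on the Minimal rates in each arm and, if 0-1 was meant, on the Mild rates too. No primary or secondary conclusion, alpha allocation or sample size depends on this variable. The conclusion that the definition is broken rests only on the SAP's own scale and needs no assumption about rates.

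**What to change.** Before unblinding, restate the entry in Section 8.5 by numeric score as one unbroken range at the favourable end, either 0-1 or 0-2, whichever the sponsor intended. Apply that definition to both doses and both visits. Naming the scores as well as the labels prevents the same ambiguity from returning.

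The cost is one line of SAP text and one line of code. No new data are needed: Section 8.4.8 derives the categories from lesion counts, and Table 4-2 already provides for imputing each lesion type, including non-inflammatory nodules.
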